Ipsilateral silent period (iSP). In order to evaluate transcallosal inhibition, we will analyze the iSP in the flexor dorsal interosseous muscle. An iSP in the affected limb is elicited by stimulating the M1 hotspot of the unaffected muscle while the paretic muscle is active. The reduction in muscle activity due to the ipsilateral stimulation is analyzed. Suprathreshold TMS is applied at 150% of the unaffected muscle's rMT (or at 100% SO, in the event of high rMT) while the subject activates their affected muscle at 20% of their maximum voluntary contraction level, monitored with visual feedback of the EMG recording. The EMG data from 10 stimuli are recorded, averaged and rectified. The iSP onset and offset are determined by analyzing the averaged, rectified data relative to a threshold determined by the pre-stimulus mean EMG value. iSP onset is defined as when the EMG falls below the threshold, and iSP offset is when the EMG returns to within 25% of the threshold for at least 50 ms[62]. We will compute both duration and the amount of EMG suppression during iSP.

Aim 2: Evaluate functional effects of myoelectric upper limb orthosis

To evaluate the functional effect of the myoelectric upper limb orthosis with powered elbow and grasp, outcome measures will include performance-based measures such as the Box and Block Test (BBT) and the Chedoke Arm and Hand Activity Inventory (CAHAI). The performance-based measures will be performed both with and without the orthosis to assess whether device usage improves function at the level of activity over time. During the period of home use, patient reported measures such as the Orthotic and Prosthetic Users' Survey (OPUS) upper extremity functional status (OPUS-UEFS) and satisfaction with device (OPUS-Sat) as well as the Revised Craig Handicap Assessment and Reporting Technique (CHART) to assess life-role participation and level of community integration will be added. The patient-reported measures will be completed to assess whether device usage at home improves perception of function and participation over time. See Table 2 for overview of schedule of assessments.

The Box and Block Test (BBT) is a standardized assessment of unilateral gross manual dexterity.

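### Item 13 averages the raw ipsilateral silent period EMG before rectifying it, which triples the noise in the suppression measure and, under light smoothing, undermines the offset rule

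*Combined protocol and SAP*

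**What the plan says.** The iSP is described in Item 13, under the outcome measures for Aim 1, as the plan's measure of transcallosal inhibition. The stimulus is given while "the subject activates their affected muscle at 20% of their maximum voluntary contraction level", so the signal of interest is an interruption of an ongoing voluntary contraction.

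The processing is stated as "The EMG data from 10 stimuli are recorded, averaged and rectified". The next sentence uses the same order: "The iSP onset and offset are determined by analyzing the averaged, rectified data relative to a threshold". That threshold is described only as "a threshold determined by the pre-stimulus mean EMG value". For onset, "iSP onset is defined as when the EMG falls below the threshold". For offset, "iSP offset is when the EMG returns to within 25% of the threshold for at least 50 ms". Two outcomes follow: "We will compute both duration and the amount of EMG suppression during iSP".

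The documents nowhere give the reverse order, a filter or smoothing window, a threshold formula, a pre-stimulus window, or a minimum duration for onset. By Item 10 and Table 2, TMS measures are compared across baseline and weeks 9, 13 and 22.

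**The concern.** Surface EMG from a voluntary contraction swings around zero, and nothing in the plan locks its phase to the TMS pulse. Averaging raw sweeps therefore shrinks the very background whose interruption defines the silent period. Rectifying each sweep first preserves that background and averages out its fluctuation. As worded, the plan takes the noisier route and then applies a rule that needs 50 ms of uninterrupted stability.

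At stake are the precision of both iSP outcomes and the number of usable durations. Item 11 plans to recruit 20 participants, and only those who pass the TMS safety criteria in Item 30 contribute. There is little room for avoidable measurement error or missing values.

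**Working it through.** The plan gives no sample size, power or numerical target for the iSP, so there is no figure of its own to reproduce.

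**Inputs from Item 13.** 10 sweeps; averaging named before rectification; background contraction at 20% of maximum; offset within 25% of threshold for at least 50 ms.

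**Assumptions not in the documents.** Gaussian EMG, independent across sweeps, band-passed 20–450 Hz and sampled at 2 kHz; a 30 ms silent period with EMG reduced to 20% or 50% of background; threshold equal to the pre-stimulus mean of the same trace; moving-average smoothing of 0, 5, 10 or 20 ms.

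**Step 1: level and noise of the background.** Let each sweep have SD s, with k = 10.
- Rectify first: mean = s√(2/π) = 0.798s; CV = √(π/2 − 1)/√10 = 0.756/3.162 = 0.239.
- Average first: mean = 0.798s/√10 = 0.252s; CV = 0.756.
- Ratio of levels: 0.252/0.798 = 0.316, a loss of about 68%.

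Simulation (1,500 runs per setting) gave means of 0.797–0.798 and 0.252–0.254, and unsmoothed CVs of 0.24 and 0.75.

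**Step 2: amount of suppression.** The silent segment shrinks by the same factor as the background, so the ratio of the two is preserved. Without smoothing, the mean residual EMG was 0.201 under both orders when the truth was 0.20, and 0.504 (average first) against 0.501 (rectify first) when it was 0.50. The SDs were 0.032 against 0.010 and 0.077 against 0.024, a ratio of 3.2 in each case, close to √10.

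**Step 3: offset rule.** The search starts just after the true onset, so these results do not depend on the onset rule. A level of 75% lies 0.25/CV trace SDs below the mean. AF is average first, RF is rectify first; ranges cover the two suppression depths; median errors are among runs in which an offset was found.

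| Smoothing | CV, AF / RF | 0.25/CV, AF / RF | Offset met (≥75%), AF / RF | Median error (ms late), AF / RF | Met on two-sided ±25% reading, AF / RF |
|---|---|---|---|---|---|
| none | 0.75 / 0.24 | 0.3 / 1.0 | 0% / 0% | – | 0% / 0% |
| 5 ms | 0.29–0.30 / 0.09 | 0.8–0.9 / 2.8 | 13% / 100% | 74.5–77.5 / 0.5–1.5 | 0% / over 99% |
| 10 ms | 0.20 / 0.06 | 1.25 / 4.2 | 71–73% / 100% | 35–40.5 / 0–2 | 10–11% / 100% |
| 20 ms | 0.13 / 0.04 | 1.9 / 6.3 | about 98% / 100% | 3.5–6 / 0–4 | 87–88% / 100% |

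Repeat simulations widened the average-first rates on the 75% reading to 11–16% at 5 ms and 71–85% at 10 ms. Rectify-first stayed at 100%.

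**Step 4: onset rule.** If the threshold is the pre-stimulus mean itself, about half of any background trace lies below it (57% average first, 52% rectify first, unsmoothed). An onset more than 5 ms too early occurred in 93–100% of runs average first and 96–100% rectify first. The order of processing is not the cause.

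**The case against.** The strongest reply is that the wording is a loose list of steps rather than a sequence. The second mention may merely repeat the first, and the automated method cited for the rule cannot be consulted here. That is possible. Even so, the text states one order twice and never the other, and an analyst following it would average first.

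A reader might go further and infer that the background is cancelled, that both outcomes become noise, and that the order is what breaks the onset and offset rules. The documents do not support this:
- About 32% of the background level remains, and mean relative suppression is unbiased when the threshold comes from the same trace.
- The onset problem arises under either order, and only if the threshold is the mean itself. Item 13 says only that the threshold derives from that mean.
- The offset contrast depends on a smoothing window that the plan does not give. With none, both orders fail; at 20 ms, on the 75% reading, both mostly work.

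The harshest case would take the threshold from single rectified sweeps (about 0.80s) and apply it to the averaged-then-rectified trace (background about 0.25s). Most of the background would then lie below threshold. The text does not exclude this, but does not say it either.

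Reordering alone is also not a complete remedy, and the data storage items never mention individual EMG sweeps, so the ability to reprocess cannot be taken for granted.

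**Conclusion.** The stated processing order is wrong as written, not merely under-described. Under the assumption that background EMG is not phase-locked to the stimulus, it costs about 68% of the background level, raises the trace CV from about 0.24 to 0.75, and triples the SD of the suppression estimate without biasing its mean. For duration, the damage is large at 5 ms smoothing and material at 10 ms, with many missing offsets and the rest typically tens of milliseconds late against an assumed 30 ms silent period. It is absent as a contrast with no smoothing and small at 20 ms on the 75% reading. The missing threshold formula and minimum onset duration are a separate weakness that affects either order.

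The change should be made, but its reach is limited. The iSP is a neuroplasticity measure; the Fugl-Meyer and Box and Block primary analyses do not depend on it.

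**What to change.** In Item 13, specify the following:
1. Rectify each of the 10 sweeps, then average the rectified sweeps. Reword both sentences that now give the other order.
2. Apply a stated smoothing window for onset and offset detection, for example 10–20 ms.
3. Define the pre-stimulus window, and set one level for onset and offset below the pre-stimulus mean of that same trace, for example 75%, the lower bound the offset rule already implies. Say whether the offset condition is one-sided.
4. Require a minimum duration below that level before an onset is declared.
5. Compute the amount of suppression from the unsmoothed trace. With a true residual of 0.20, smoothing moved the rectify-first estimate to 0.233, 0.266 and 0.333 at 5, 10 and 20 ms.
6. Retain the individual sweeps.

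The cost is a few sentences in Item 13 and a change of analysis settings; no visit or procedure changes. Two limits should be noted. If averaging is done at acquisition and single sweeps are not kept, data already collected cannot be reprocessed. A 75% level will also not register suppression shallower than 25%, so the plan should say how such recordings are handled. If the laboratory already rectifies first, the edit simply brings the plan into line with practice.

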#### 30. Please list by bullet point inclusion/exclusion criteria for the study.

- Entry criteria should be as detailed as necessary to define the subject population(s) under study and reduce confounding design. Include precise criteria for age, gender, and other relevant factors.
- List specific exclusion criteria which could interfere with the study design or place a subject at risk during the study.
- Provide answers for each cohort, including normal controls

#### INCLUSION CRITERIA.

- Over 18 years of age
- Minimum 6 months since injury or stroke
- Full passive range of motion at the elbow, forearm, wrist, and hand [26]
- Active shoulder flexion of at least 30 degrees and active shoulder abduction of at least 20 degrees
- Minimum of 1/5 on manual muscle test of elbow flexion and extension (biceps and triceps) [26] and forearm flexors and extensors
- Ability to generate volitional, consistent, and detectable EMG signals from the upper arm and forearm sensor sites with wrist in neutral or flexed positions as detected by the MyoPro Motion-G software
- MAS score  $\leq 3$  for the biceps, triceps, supinators and pronators of the impaired arm
- Able to read and comprehend the English language
- Demonstrate ability to follow two-stage command
- Cognitive abilities sufficient to perform testing and training protocols
- Able to tolerate functional tasks for 60 minutes without excessive fatigue [26]
- Medically and psychologically stable [26]
- At home support from a family member or care giver if needed [26]

#### **EXCLUSION CRITERIA:**

• Spasticity of both the flexors and extensors (defined as > 3 on MAS for both) and also the shoulder internal rotators [26]

- Shoulder subluxation, pain or dislocation
- Shoulder passive range of motion < 45 degrees in flexion and abduction
- Fixed upper limb contractures on the impaired arm and hand
- Unable to safely support the weight of their arm plus 4 lbs (1.82 kg) (the weight of the device) without pain
- Unable to safely bear a torque of 14 Newton Meters (Nm) or less on their elbow
- Less than 12 weeks since botulinum toxin injection in the impaired arm [26]
- New therapies/medications planned during study period
- Skin rash or open wound on impaired arm [26]
- Absent sensation (light touch or pain) on impaired arm
- Involuntary movements of the impaired arm [26]
- Pain or hypersensitivity in the impaired arm
- Inability to understand English

#### EXCLUSION CRITERIA for MRI OUTCOME MEASURE

- Pregnancy or pregnancy planning during the study period
- Inability to tolerate MRI or contraindications for MRI

#### EXCLUSION CRITERIA for TMS OUTCOME MEASURES

- Presence of implanted medical devices such as cardiac pacemakers and defibrillators, intrathecal drug delivery pumps, or spinal cord, vagus nerve or similar stimulators, or cochlear implants [65]
- Presence of metallic hardware that would be in close contact with the TMS discharging coil such as intracranial implants, aneurysm clips, plates, electrodes
- Past history of seizures
- History of substance abuse within the last 6 months
- Recently stopped taking the following drugs within the past 6 months: barbiturates, benzodiazepines, meprobamate and chloral hydrate
- Currently taking medications or substances that significantly lower the threshold for onset of seizure [65]

1	 TAT / A	~ // *	, .
ı	 N/A	t hart/d	oto romiow
ı	 11/2	Chai yu.	ata review

31. By role, (PI, Coordinator, etc.) who will assess for eligibility and how will this be accomplished?

After consent for screening is obtained, the Study PI, therapist and study staff will screen the candidates. They will meet and review the screen data. PI will contact candidate's medical provider as necessary. Study PI in consultation with a physical therapist and study staff will make a decision regarding subject's eligibility.

32. Are any subjects excluded on the basis of race, ethnic group, understanding of English, socioeconomic status, education, gender, or pregnancy?

• Note: It is appropriate to indicate that you do not anticipate encountering do not speak English based on the population to be studied	potential subjects who
No	o ensure safety of the
☐ N/A Chart/data review	
33. Will subjects be reimbursed or paid an incentive for participating?	•
No (skip to item #35)	
☐ N/A Chart/data review (skip to item #38)	
34. How and when will they be paid?	
Cash Check Other -please explain:	
☐ Prorated -provide schedule: ☐ Fixed -provide schedule	
35. Will subjects be responsible for any of the costs related to the research?	
No ☐ Yes- please explain:	
36. Will treating physicians, clinicians, or researchers be compensated or paid an incentive for referring or enrolling subjects?	
No	
37. Please describe steps you will take to ensure that subject selection is fair a	nd equitable:
1. There are no restrictions regarding inclusion of women and minorities in will exclude subject from having TMS and MRI outcome measures collecte	•
2. All potential study subjects will be evaluated using the defined inclusion	exclusion criteria.
Section 5 – Risks and Benefits	
38. Please list by bullet and describe the reasonably foreseeable physical, psyceconomic, and privacy risks, side effects, or discomforts associated with the expected frequency and severity.	
• If this study is a retrospective chart review, or involves only the analysis of present in the form of data security concerns.	of data, risk may still be
Risk Assessment	

Potential Foreseeable Risks-orthosis and study treatment/testing procedures

Prolonged duration of the study.

Discomfort/pain from wearing the orthosis.

- Failure of the safety mechanisms of the orthosis.
- Sensitivity to materials of the orthosis or electrodes.
- Loss of confidentiality
- Fatigue during study interventions.
- Muscle soreness from exercising weak/deconditioned muscles
- Lying Quietly In A Confined Space and Loud Noise during MRI testing
- Mild risk of developing a headache during TMS testing
- Discomfort during EMG
- Unforeseeable Risks

Although the myoelectric arm brace has been used since 2007 in both studies and clinical practice, it is possible that there may be other risks that we cannot predict.

• Risks of data security breach

## \*Certificate of Confidentiality:

- Certificates of Confidentiality are issued by the National Institutes of Health (NIH) to protect identifiable research information from forced disclosure.
- They allow the investigator and others who have access to research records to refuse to disclose identifying information on research subjects in any civil, criminal, administrative, legislative, or other proceeding, whether at the federal, state, or local level.
- Certificates of Confidentiality may be granted for studies collecting information that, if disclosed, could
  have adverse consequences for subjects or damage their financial standing, employability, insurability, or
  reputation.
- By protecting researchers and institutions from being compelled to disclose information that would identify research subjects, Certificates of Confidentiality help achieve the research objectives and promote participation in studies by assuring confidentiality and privacy to subjects.
- For more information, see http://grants1.nih.gov/grants/policy/coc/index.htm.

39.	attitudes, use of drugs or addictive products, and illegal conduct that would need to be protected against subpoena or forced disclosure in order to protect subjects?	
	⊠ No	
	Yes- will an application for a *Certificate of Confidentiality be submitted to the National Institute of Health upon IRB approval (or approval contingent on the issuance of such a certificate)?	
obt	Yes No provide a justification as to why a Certificate of Confidentiality will not be ained:	

# 40. Describe all procedures that minimize risks, please include study and standard of care procedures:

# Procedures that minimize Potential Foreseeable Risks-orthosis and study treatment/testing procedures

- The total duration of the study is about 31 visits over a period 22 weeks, which is a long commitment and increases risk of subject dropout. Subjects are informed of their time commitment during the screening phase and at enrollment consent and throughout their study participation.
- There is a possibility that some discomfort may arise while wearing the orthosis. Subjects will be required to wear the device for up to two hours during training and as long as tolerated at home. If at any time they feel uncomfortable, they are instructed to inform the researchers so that modifications can be made to the orthosis to improve comfort.
- There is a possibility that if the subject had ever experienced issues with shoulder instability or pain using the orthosis may cause these issues to flare up again Shoulder stability and pain will be monitored throughout the study to ensure that the device is not causing problems. Development of shoulder pain or additional subluxation during the course of the study would result in subject withdrawal from the study if modifications such as adding a shoulder harness were insufficient to overcome shoulder stability issues.
- The manufacturers of the orthosis have been careful to ensure that it is safe and cannot apply a dangerous amount of force to the arm or hand. Safety mechanisms have been implemented into the control software, the electronics hardware, and the mechanical hardware of the brace. For example, in the software commands that control the orthosis and the electronics of the orthosis, there are limits on the amount of force that can be commanded to the system. The mechanical system contains physical limits that prevent the orthosis from exerting force in an unsafe direction. In the worst case scenario, if all of these safety mechanisms fail, there is a small risk that the arm could be injured.
- The orthosis incorporates stainless steel, non-allergenic surface electrodes with no adhesive. It is very rare that these electrodes will cause skin irritation, but they might if the subject has allergies to certain metals (not including nickel) and/or orthosis fit is not correct. Development of skin rashes or open wounds as a result of the orthosis that could not be overcome by modifications to fit or improved donning/doffing procedures would result in subject withdrawal from the study.
- Functional performance of the arm with the orthosis will be videotaped during some of the outcome evaluations. The subjects' upper body, head, and neck will be visible in the video tapes which increases the risk of loss of confidentiality. The tapes will be stored in a locked cupboard. The only people with access to the cupboard will be the treating therapist and [name].
- Fatigue during study interventions. During the therapy sessions and testing sessions, subjects could become fatigued during a given motor learning session. Subjects could experience mild muscle soreness associated with using muscles that have not been utilized for a number of months or years. Exercises will be progressed to patient tolerance and monitored both within and between sessions by the therapist.
- Risk management and emergency response
  - Subjects will be monitored at all study visits to ensure that there are no open wounds or skin rashes on the impaired arm and that the shoulder is not dislocated, subluxed or painful. If at any time during the use of the device, the subject notices any of the following, they should immediately discontinue use and seek guidance from the researchers:
  - Unusual noises from the orthosis (skipping, clicking, etc.)
  - Smells from the orthosis (smoking, burning plastic, etc.)

The investigators may stop a subject's participation in the study without their consent if they think that it will be in the best interest of the subject, if the subject does not follow the study plan, if the subject experiences a study-related injury, or for any other reason. If subjects sustain an injury as a direct result of the study, medical care will be provided by the Cleveland VA Medical Center at no cost to the subject. Financial compensation for such things as lost wages, disability, or discomfort due to an injury is not available.

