#### 10. Describe the means of analyzing the data and evaluating the results.

- State the anticipated methods to be used for analysis and interpretation of the data.
- The methods must compliment the design of the study and the nature of the data which is being collected.

As a primary analysis of therapeutic benefit, we will use a paired t-test to compare the difference between baseline and final evaluation at the end of the home use period. A similar comparison using the Box and Block Test results will be used as the primary analysis of functional benefit. For these primary analyses, critical alpha will be adjusted using the Bonferroni correction to account for Type 1 error.

Secondary analyses will assess changes over time in each outcome measure as well as correlations between satisfaction and measures of motor impairment and function (both perceived and actual). We anticipate that the therapeutic measures will increase initially before plateauing while functional measures are expected to increase slowly at first with

continued gains across the home use period. We expect that satisfaction will be positively correlated with perceived improvements in function.

We will use single subject analysis to evaluate changes over time for each outcome measure. In order to capture individual effects, baseline to end of home use outcomes data will be plotted, with outcome measure score on the vertical axis and time/transition through conditions (therapy/training to home use) on the horizontal axis. Visual inspection in the form of change in trend (i.e., a systematic variation in the slope of the data points from one phase to the next) will be used. [name] has some experience with single subject analyses as detailed in a paper accepted for publication that evaluated ankle foot orthoses effect on community ambulation outcomes in children with cerebral palsy.

Spearman's correlation will be used to assess the relationship between OPUS satisfaction with device and Fugl-Meyer Assessment of Motor Recovery upper limb subsection score, as well as OPUS satisfaction with device and OPUS functional status.

As a primary analysis of MRI-based measures, we will use a paired comparison between baseline and post training evaluation (prior to home use period). For the TMS-based measures, we will compare data between baseline, at week 9, after the end of the therapy and after the end of the home-use phase. We will evaluate changes over time for each outcome measure.

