Study Part 2 – Orthotic Fitting: Myomo will provide three MyoPro Motion-G devices to be used through-out the study and the fit of each device will be customized for each subject. These devices will be used on a rotating basis during the study period which means that at the end of the participation in the study, a subject will return the MyoPro-G device to PI. A Certified Orthotist from either the Cleveland VA or from Myomo will custom fit all orthoses individually to each subject for optimum performance. This process will require up to three visits to cast, trial fit and deliver the orthosis.

During the fitting process, first a plaster mold of the subject's arm will be taken. This mold is used for custom orthosis construction and fabrication typically takes 2 weeks. Once the orthosis has been constructed, the subject will be brought back for a fitting. During this fitting, the device will be calibrated to the subject's individual muscle signal profile and minor adjustments to the orthosis can be made to optimize comfort.

Subjects will receive both powered elbow and grasp at the same time. Throughout the duration of the study, the study orthotist will be available once a week to check the fit of the device and troubleshoot any device issues as needed.

The MyoPro is a relatively new, commercially-available custom fabricated upper limb orthosis that is individually fabricated for the patient over a positive model of the patient requiring education, training, and experience to custom-fabricate. It has been cleared by the Food and Drug Administration (FDA) for home use without direct supervision of a therapist [26]. The

MyoPro Motion G features include a lightweight elbow orthosis with a surface electromyography (sEMG) sensor, a lightweight hand orthosis with a sEMG sensor, a "motion W" manually set multi-articulating wrist and a rechargeable battery. MyoPro's sEMG controlled software continuously monitors and senses, but does not stimulate, the affected muscles. The system then filters and processes data, which is sent to a motor to enable the desired motion. The process is similar to the way power steering helps a driver maneuver a car. Based on the subject's abilities, the system parameters are adjusted by the therapist or orthotist. The power assist only applies an amount of force proportional to what users exert naturally; this encourages them to apply and maintain all the strength and control they have to achieve a range of motion.

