	X	assessed with	out orth	osis; O	assesse	d with or	thosis			
Passive ROM	X	X	X	X	X	X	X	X	X	X
Active shoulder ROM	X		X	X	X	X	X	X	X	X

MMT	X		X				X	X	X	X
EMG signal	X		X				X	X	X	X
MAS	X	X	X	X	X	X	X	X	X	X
Read English	X									
Shoulder subluxation, pain, dislocation Skin rash/open wounds	X	Ongoing r subluxation such as addir	would r	esult in	subject w ness was	vithdrawa	al from t	he study	if modif	ications
Monofilament	X	X	X		X		X	X		X
		Per	forman	ce-Base	l Measu	res				
Wrist Position Sense Test		X	X		X		X	X		X
Fugl-Meyer		X	XO	XO	XO		XO	XO	XO	XO
BBT		X	XO		XO		XO	XO	XO	XO
CAHAI		X	XO		XO		XO	XO	XO	XO
		Pa	tient-Re	eported	Measure	es				
OPUS-UEFS		X					X			X
OPUS-Sat		X					X			X
CHART		X					X			X
MRI		X					X			
TMS (MEP-rc/iSP		X			X		X			X
H-reflex		X			X		X			X

14. Will the research involve the following?

	□ N/A Chart/Dat	a Keview	
	Placebo Group	⊠ No	☐ Yes (describe):
	Other Control Group	p 🛮 No	Yes (describe):
	Randomization	⊠ No	Yes (describe):
	Deception	⊠ No	Yes (describe):
	Information in any fo ☐ No ☐ Yes	orm or mediun  If yes, com	nd/or disclosure of Individually Identifiable Health n?  uplete the required HIPAA Waiver/Authorization forms.  ration of a study agent that does not require FDA approval
. 0.	v		itamins, food supplements, isotope tracers, alternative
	⊠ No ☐ Yes	s -provide a deta	ailed description of the procedures used to assure patient safety:

17.	Will radioactive material be administered or will subjects be exposed to ionizing radiation?
	
 
Ex. Radiographic equipment, fluoroscopic equipment, and CT scanners, etc.
 
No ☐ Yes
 

18.	In your judgment, could the objectives of the research be met in a way that presents less risk to subjects?
	No ☐ Yes please explain:
	Section 4 – Subject Selection, Recruitment, and Vulnerable Populations
19.	Anticipated duration of entire study reported in years: 6 years or till July 2022
20.	Estimated number of subjects to be studied at the LSCDVAMC or charts/records to be reviewed.
	• Provide answers for each cohort including normal controls; (patients, family members, treating physicians,):
	70 TBI or stroke subjects to enroll 20
21.	Estimated number of subjects to be studied or charts/records to be reviewed at all sites
	
 
Provide answers for each cohort including normal controls; (patients, family members, treating physicians,)
 

	N/A SINGLE SITE
22.	Duration of individual subject participation

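### Unresolved shoulder or orthosis-related skin problems end study participation, not only device use, so these subjects lose the week-22 value; keeping the no-orthosis visit would be a cheap improvement

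*Combined protocol and SAP*

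**What the plan says.** Item 40 has two withdrawal rules. Shoulder pain or additional subluxation "would result in subject withdrawal from the study if modifications such as adding a shoulder harness were insufficient to overcome shoulder stability issues". Skin rashes or open wounds due to the orthosis that "could not be overcome by modifications to fit or improved donning/doffing procedures would result in subject withdrawal from the study". The shoulder rule is repeated in Item 13, Table 2, in the row labelled "Shoulder subluxation, pain, dislocation Skin rash/open wounds". The text of that row is damaged, and the legible part supports withdrawal for the shoulder only.

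No section plans an assessment after withdrawal. Item 66 says only that leaving early carries no risk. Item 40 does have wording for stopping the device alone (unusual noises or smells), but does not use it for these events.

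For therapeutic benefit, Item 10 states: "we will use a paired t-test to compare the difference between baseline and final evaluation at the end of the home use period". For functional benefit, the primary analysis applies the same kind of test to the Box and Block Test (BBT). Neither Item 10 nor Item 11 gives an analysis set or a method for missing values.

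Item 13 has the Aim 1 measures, including Fugl-Meyer, taken without the orthosis, and the BBT taken both with and without it. Table 2 schedules both tests without the orthosis at baseline and at week 22.

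**The concern.** The subjects removed by these rules are the ones in whom a device problem could not be solved, so their absence from the paired comparison is related to the intervention. The study has a single group, and no comparison arm could reveal the effect of that selection. If withdrawn subjects gain less than completers, the reported mean change is too high. If they gain the same, it is unaffected. If problems arise mainly in heavy users who gain most, it is too low.

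The loss is avoidable, because a no-orthosis Fugl-Meyer or BBT does not require wearing the device. Once week 22 has passed, the value cannot be recovered.

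**Working it through.** **Inputs.** Item 11: pilot change in Fugl-Meyer 3.2, SD 2.91; d = 1.107; one-tailed paired t-test; alpha 0.05; power 0.95; n = 11; recruit 20. Item 10: Bonferroni over two primary analyses, taken here as one-sided 0.025 each. Fugl-Meyer is taken as the therapeutic primary because Item 11 sizes the study on it. The documents give no rate for these withdrawals, so k = 1 or 2 of 20 fitted subjects is an assumption.

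**The plan's own figure.** Power = P(T > t_crit), where T is noncentral t with n − 1 degrees of freedom and noncentrality d√n. For n = 11, noncentrality is 1.107 × √11 = 3.67 and power is 0.961. For n = 10 it is 0.943. So 11 is reproduced.

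**Power after losses.** At d = 1.107 and one-sided alpha 0.025, power is 0.997 with 20 pairs, 0.995 with 19 and 0.993 with 18.

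**Shift in the completers mean.** Shift = (k/20) × (completer mean − withdrawn mean), with completer mean 3.2.

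| k | Withdrawn gain 0 | Withdrawn gain 3.2 | Withdrawn gain 6.4 |
|---|---|---|---|
| 1 | 0.05 × 3.2 = +0.16 (all-subject mean 3.04) | 0 | −0.16 (mean 3.36) |
| 2 | 0.10 × 3.2 = +0.32 (mean 2.88) | 0 | −0.32 (mean 3.52) |

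The shift is proportional to k, so 4 of 20 would give up to 0.64 either way. Zero gain is an extreme assumption, since a withdrawn subject may already have had weeks of therapy.

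**Scale.** 0.16/2.91 = 0.055 of the pilot SD. The standard error of the mean change is 2.91/√19 = 0.668 with 19 pairs and 2.91/√18 = 0.686 with 18. So 0.16 is 0.24 of a standard error and 0.32 is 0.47 of one. The full scale is 66 points.

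**Effect on the test at the zero-gain extreme, k = 2.** Completers: t = 3.2/0.686 = 4.67. All 20, with two changes of exactly zero: sum of squares = 17 × 2.91² + 18 × 0.32² + 2 × 2.88² = 162.4, SD = √(162.4/19) = 2.92, and t = 2.88/(2.92/√20) = 4.41. The one-sided 0.025 critical value is 2.09 on 19 degrees of freedom. The conclusion is the same either way.

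**What survives withdrawal.** Table 2 also has no-orthosis Fugl-Meyer at weeks 5, 7, 9, 13, 16 and 19, and BBT at weeks 5, 9, 13, 16 and 19. Scores taken before withdrawal can enter the secondary change-over-time analyses. Only the end-of-home-use pair is lost.

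**The case against.** **Few events are likely.** This stands. Item 30 excludes at entry "Shoulder subluxation, pain or dislocation" and "Skin rash or open wound on impaired arm". Under Study Part 2 of Item 13, "the study orthotist will be available once a week to check the fit of the device and troubleshoot any device issues as needed". Withdrawal follows only when modification fails. Item 40 also says "It is very rare that these electrodes will cause skin irritation", though that concerns the electrodes, not the shoulder or the fit of the brace. The cost of the extra visit falls in step with the number of events.

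**Twenty are recruited and 11 are needed.** That protects power at the planning effect size. It does not address who is missing.

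**The rule is not what makes this a completers analysis.** A reader might infer that it is. A paired t-test with no missing-data method omits anyone without a final value, whatever the reason. Item 40 itself names the length of the study as a dropout risk and lets investigators end participation for other reasons. The two rules add one source of selection, and changing them leaves the others in place.

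**The remedy changes the question.** This stands in part. Item 9 aims to document outcomes in Veterans using the orthosis, and someone who stopped during therapy has no home-use period on the device. Whether such subjects belong in the primary result or beside it is a choice of estimand on which statisticians can differ.

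**The recovery is partial.** This also stands. Item 10 does not say whether the BBT primary is with or without the orthosis; if with, the visit cannot supply the missing value. Fugl-Meyer scores shoulder movement, so some painful shoulders cannot be tested validly. A week-22 score after stopping may mix partial device exposure with other care.

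**Conclusion.** The point holds as a cheap improvement. Both rules in Item 40 remove the subject from the study, and no later assessment is planned, so subjects withdrawn before week 22 lack the value that the paired comparison needs. On the assumption of 1 or 2 withdrawals among 20 fitted subjects, with a mean gain within 3.2 points of the completers' mean, the shift is at most 0.16 or 0.32 Fugl-Meyer points in either direction. That is under half a standard error, with negligible loss of power.

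A reader might infer that the primary result will be inflated. The documents do not support that: they give no withdrawal rate and no information on how withdrawn subjects change, and the shift could be zero or negative. Nor can Table 2 be cited for the skin rule, which rests on Item 40 alone. The case rests on low cost and on a clearer account of subjects who could not tolerate the device, not on a demonstrated bias.

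**What to change.** In Item 40 and the matching row of Table 2, replace withdrawal from the study by stopping the orthosis, with the stopping criteria unchanged. Obtain the no-orthosis Fugl-Meyer and BBT at the already-scheduled week-22 visit in consenting subjects who can be tested safely, and record any other therapy received after stopping.

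In Item 10, report the paired change in all fitted subjects with a week-22 value next to the result in those who completed home use, and state beforehand which is primary. For BBT, this applies only to the no-orthosis comparison. Report how many stopped for device problems and how many of those were tested.

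The cost is a short amendment to Items 10, 13 and 40, possibly a consent-form change, and one existing visit for probably few subjects. Some will decline or be untestable, and the mean change may come out smaller.
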